## 9 STUDY TREATMENT AND DOSING

## 9.1 STUDY MEDICATION (TAVT-18 SIROLIMUS)

The half-life of sirolimus (TAVT-18) is estimated to be >30 hours, allowing for convenient twice daily oral dosing. Medication should be taken in the fed state, defined as within 30 minutes of feeding. An individualized PK model-informed age-adjusted dosing scheme with a starting dose based on age at the time of enrollment (see Table 2) will be utilized, which is based on previous experience and simulation analysis of data obtained from our previous studies treating infants with congenital vascular anomalies with RapamuneTM 49, 77, 82 and preclinical and human studies with TAVT-18. These targeted doses are estimated based on the assumption that the oral bioavailability of TAVT-18 is 2-times higher compared to RapamuneTM. The target pre-dose whole blood trough sirolimus concentration (Cmin) will be 10 ng/mL with an upper tolerance range of 10-15 ng/mL. This target is consistent with prior published experience from infants treated with sirolimus for clinical indications and previous clinical trials in TSC patients treated for SEGA or epilepsy.

Table 2: Estimated	l sirolimus (TAVT-18) starting doses for the indicated target
concentration rang	ge 
Age group	Dosing for target concentration range = 10-15 ng/ml

(months)	
0-1	$0.2 \text{ mg/m}^2/\text{dose}$ , administered twice daily (total daily dose = $0.4 \text{ mg/m}^2$ )
1-2	$0.25 \text{ mg/m}^2/\text{dose}$ , administered twice daily (total daily dose = $0.5 \text{ mg/m}^2$ )
2-3	$0.3 \text{ mg/m}^2/\text{dose}$ , administered twice daily (total daily dose = $0.6 \text{ mg/m}^2$ )
3-4	$0.35 \text{ mg/m}^2/\text{dose}$ , administered twice daily (total daily dose = $0.7 \text{ mg/m}^2$ )

4-6	$0.45 \text{ mg/m}^2/\text{dose}$ , administered twice daily (total daily dose = 0.9 mg/m 	5

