Steady state whole blood trough levels should be drawn in the morning, approximately 24-hours since last dose of study medication, after the subject has been on continued dosing for 7-14 days. Sirolimus trough level may be drawn at the participating study center or drawn locally and sent to the reference laboratory, whichever is easier for the subject. Subjects for which treatment is held temporarily due to an AE but resumed at same dosing as prior to the AE (see section 12) do not require a repeat sirolimus whole blood trough level to be checked when resuming treatment after the AE has resolved.

Whole blood sirolimus trough levels will be assessed at defined intervals after the initial dose (+1, +3, +6, +24 hours). Infants will continue daily dosing at the same dose, orally twice/daily within 30 minutes of feeding, for an additional 6 days  $(\pm 1 \text{ day})$ , when the steady state sirolimus whole blood trough levels will be assessed at defined intervals of +1, and +3 hours post-dose. Based on resultant steady-state measured trough level at day 7, sirolimus dosing will be adjusted per protocol (see next paragraph) to achieve the desired precision dosing target of 10 ng/ml. Treatment at the adjusted dosing will continue an additional 6 days  $(\pm 1 \text{ day})$ , after which the steady state sirolimus trough level will be measured again (day 14). Subject recruitment and participation is an essential component to the success of the overall study, but it is recognized enrollment is unlikely unless given opportunity to continue treatment beyond 14 days given the potential for direct benefit (see section 6.2 above) provided no individual- or group-level safety concerns are encountered. Accordingly, after the day 14 sirolimus trough level, participants can elect to continue open-label treatment with TAVT-18 (sirolimus) up to 12-months of age, providing additional extended exposure dosing and safety data for TAVT-18. For additional details, see section 11.2 below.

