## 11.2 Initial Open-label PK Study (Stage 1)

Five infants will be enrolled for detailed TAVT-18 (sirolimus) dosing and pharmacokinetic (PK) analysis and preliminary safety profile. Open-label, non-randomized treatment initially will be for 14 days, during which sirolimus trough levels and safety labs will be collected at baseline and at defined intervals along with continuous AE/SAE reporting.

Following verification of baseline safety laboratory studies (CBC with differential, complete metabolic panel, lipid profile, amylase, and lipase), initial dosing will be based on age at the time of enrollment (see Table 2), dosed orally within 30 minutes of feeding, twice/daily (see section 9.1). Whole blood sirolimus trough levels will be assessed post-dosing at defined intervals (+1, +3, +6, +24 hours) on day 1. Infants will continue daily dosing at the same dose, orally twice/daily within 30 minutes of feeding, for an additional 6 days ( $\pm 1$  day), when the steady-state sirolimus whole blood trough level will again be assessed at +1 and +3 hours post-dose. Based on resultant steady-state measured trough level at day 7, sirolimus dosing will be adjusted per protocol to achieve the desired precision dosing target of 10 ng/ml (see section 9.1). Dosing will continue for an additional 7 days and the final PK assessment for Stage 1 analysis will be assessed on day 14 ( $\pm 1$  day). Safety labs will be repeated at the +7 days and +14 days assessment visits. In addition, AE and SAE safety data will be collected throughout.

Subjects with no significant AE/SAE during the initial 14-day treatment period will be allowed to continue open-label treatment so as to allow collection of additional extended exposure safety data until 12 months of age, provided sirolimus trough levels within the target range are able to be achieved and maintained (see section 9.1 above).

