## 11.3 Interim Analysis and DSMB Determination of Study Continuation

After the last (5th) subject completes the 14-day open-label treatment study visit, a detailed PKdosing and preliminary safety analysis report will be prepared by the study team for review by the study sponsor, drug supplier, and DSMB. Specific criteria for continuation of the study (Go/No-Go criteria) are not specified for this Phase I study, but the report must address the following key questions to the DSMB's satisfaction:

- (1) Is 0.2-0.45 mg/m^2 TAVT-18 (sirolimus) dosed orally 2x/day appropriate for initial dosing in TSC infants 0-6 months of age to achieve a target sirolimus trough levels between 5-15 ng/ml?
- (2) Does the proposed real-time, individualized PK model-based precision-dosing strategy for TAVT-18 (sirolimus) in TSC infants perform adequately in order achieve the target steady-state sirolimus trough level of 10 ng/ml?

- (3) Are there any unique safety events or related concerns that have emerged in TSC infants that were not anticipated which significantly alter the potential benefit-to-risk profile for TAVT-18 (sirolimus) in this population?
- (4) Have any practical issues with the planned study design been identified which were not anticipated that could impact the feasibility or successful completion of the primary objectives of the study?

The DSMB may request additional information or analysis from the investigators, modification to the study design, or study discontinuation.

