#### **TABLE 3: Schedule of Study Procedures/Events**

Neuropsych assessment 						Х	Х
Dispense Study Drug	Х	Х	Х	Х	Х		
Interim phone vists 							

Subjects may be enrolled into the study at any time between the ages of 0-6 months and will receive TAVT-18 (sirolimus) until 12 months of age. Visit window for follow-up visits is  $\pm 2$  weeks.

Includes option for additional bloodwork for exploratory measures; subjects not taking study medication within the previous 48 hours of the study visit due to AE or other reasons will not have sirolimus level assessed.

Sirolimus trough levels should be drawn in the morning, approx. 24hrs after last dose of study medication. The initial level will be drawn 7-14 days after subject has been on steady dosing and in conjunction with safety labs at each clinic follow-up visit (1,3,6,9,12 mths). Similarly, trough levels will be drawn at 7-14 days after any dose modification, until target concentration is reached. For convenience, levels can be drawn at the study center or drawn locally and sent to the reference laboratory.

Routine EEG (60 minutes duration). EEG acquisition schedule for study is consistent with current TSC clinical guideline recommendations dMRI is 15-minute add-on sequence to conventional MRI that is recommended clinically every 1-3 years in TSC.

Developmental assessment consists of TAND Checklist, VABS, and Bayley-4 at the 12 months of Age visit and TAND Checklist, VABS, Bayley-4, PLS-5, and ADOS-2 at the 24 months of Age visit

Monthly calls will occur in between in-person visits. During the first month in the study, phone calls will occur weekly.

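### With twice-daily dosing and a pre-dose trough target, the instruction to draw the trough about 24 hours after the last dose cannot be met unless a dose is skipped, and the resulting level would read below the target quantity

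*Combined protocol and SAP*

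**What the plan says.** Section 9.1 describes the half-life as more than 30 hours, "allowing for convenient twice daily oral dosing". The quantity to be controlled is the "target pre-dose whole blood trough sirolimus concentration" (Cmin), which "will be 10 ng/mL with an upper tolerance range of 10-15 ng/mL". On this schedule, pre-dose means about 12 hours after the previous dose.

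The sampling instruction, also in section 9.1, is different: "Steady state whole blood trough levels should be drawn in the morning, approximately 24-hours since last dose of study medication". Table 3, footnote 2, repeats it: "trough levels should be drawn in the morning, approx. 24hrs after last dose of study medication".

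The measured level is then set against target in several places:

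- Table 3, footnote 2: "trough levels will be drawn at 7-14 days after any dose modification, until target concentration is reached".
- Section 11.2 allows open-label treatment to continue after day 14 "provided sirolimus trough levels within the target range are able to be achieved and maintained".
- Section 11.3, question 1, asks the DSMB whether the starting doses are suitable "to achieve a target sirolimus trough levels between 5-15 ng/ml". Question 2 asks whether the individualized dosing reaches a steady-state trough of 10 ng/mL.
- Section 4.2, item 3, makes the steady-state trough a secondary endpoint.

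**The concern.** A 24-hour gap before the draw requires the evening dose before it to be omitted. No part of the document asks for that: sections 9.1 and 11.2 have twice-daily dosing continue up to the day 7 assessment. The draw instruction and the dosing schedule therefore cannot both be followed, and a level drawn as instructed is not the Cmin that the target describes.

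Verifying the dose is the main job of this five-infant study. If some levels are taken at 24 hours and read as if they were pre-dose values, an infant who is on target looks under-dosed, and one who is above the upper limit can look in range. Section 9.1 also allows levels to be drawn locally, which makes it more likely that the conflict is resolved differently from one draw to the next.

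**Working it through.** **Inputs.** Dosing is nominally every 12 hours (section 9.1 says twice daily). The target is 10 ng/mL pre-dose, with an upper tolerance of 10–15 (section 9.1); DSMB question 1 uses 5–15 (section 11.3). The half-life is given only as above 30 hours, with no upper bound and no infant value. The 60-hour figure below is an assumption used to show a range. The plan states no ratio of 24-hour to 12-hour levels, so it has no figure of its own to reproduce.

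**Formula.** If the evening dose is omitted, the level decays for a further 12 hours. With half-life h in hours, the 24-hour level as a fraction of the 12-hour pre-dose level is r = 2^(−12/h). A true trough C reads as C × r, and a reading R means a true trough of R / r.

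| Half-life | r | Reading if true trough is 10 | True trough if reading is 10 | True trough if reading is 15 |
|---|---|---|---|---|
| 30 h (stated lower bound) | 0.758 | 7.6 | 13.2 | 19.8 |
| 60 h (assumed) | 0.871 | 8.7 | 11.5 | 17.2 |
| 72 h (assumed) | 0.891 | 8.9 | 11.2 | 16.8 |
| 100 h (assumed) | 0.920 | 9.2 | 10.9 | 16.3 |

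**Check.** Superposing 12-hourly doses to steady state in a one-compartment oral model, with the next dose omitted and absorption rates of 0.5, 1 and 2 per hour, gives 0.758–0.759 at 30 hours and 0.871 at 60 hours. The simple formula is adequate.

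**At the limits of the ranges, for 30 and 60 hours.**

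- Upper limit: a true trough of 15 reads 15 × 0.758 = 11.4 or 15 × 0.871 = 13.1. Readings from there up to 15 would look in range while the true trough is above 15.
- Lower limit of question 1: a reading of 5 means a true trough of 5 / 0.758 = 6.6 or 5 / 0.871 = 5.7. True troughs between 5 and that value would read below range.

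**If infants have a shorter half-life.** At 24 hours r is 0.707, and a reading of 10 means 14.1. At 20 hours r is 0.660, and a reading of 10 means 15.2. Titrating a 24-hour reading to 10 would take the true trough above 15 only if the half-life were under 12 / log2(1.5) = 20.5 hours.

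**With the draw moved to just before the morning dose,** r is 1 whatever the half-life.

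**The case against.** The strongest reply is that the bias may never occur. Since no one is told to skip a dose and the target is explicitly pre-dose, staff may simply draw in the morning before dosing, about 12 hours after the evening dose, and the level is then right. Section 10.3 also mentions separate dosing instructions for families, which are not part of the document. This stands: the bias depends on a dose actually being skipped. But it amounts to relying on staff to depart from a rule that is written twice.

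The second reply is that dosing does not rest on raw readings. Section 9.1 uses a Bayesian population model and a diary of exact dose times. Sections 10.3 and 11.6 put dose time and amount on the CRF at each draw. A model fed with actual times handles a 24-hour level correctly. This stands too, for the Bayesian dosing and for the population modelling in section 16.1. It does not cover the repeat-draw rule, the continuation condition, the DSMB questions or the trough endpoint, because none of these says that a level is first converted to a 12-hour value. Nor does any say that it is not. Section 11.3 also sets no go/no-go threshold, so no formal decision turns on a reading near a limit.

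Third, the size is uncertain. The half-life above 30 hours is cited to a study in healthy volunteers, and section 3 warns that clearance can vary significantly in very young children. A reader might infer a known bias that one factor could correct. The documents do not support that: the direction is known if a dose is skipped, but the amount depends on each infant's half-life.

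**Conclusion.** The draw instruction is wrong as written, and the severity is minor. Twice-daily dosing, a pre-dose target and a draw at about 24 hours are incompatible, and the text does not reconcile them. The day 1 sample at +24 hours does not do so, because it is timed from the initial dose.

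If the instruction is followed literally, the level is about 76% of the pre-dose trough at a 30-hour half-life, about 87% at an assumed 60 hours, and closer to 100% beyond that. If the draw is made before the morning dose with nothing skipped, there is no bias. The practical risk is then an unmarked mixture of 12-hour and 24-hour levels.

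A reader might infer that infants would be dosed above range. The figures do not show that. For half-lives of 30 hours or more, even titrating a raw 24-hour level to 10 ng/mL leaves the true trough at about 13.2 or less, inside the 10–15 tolerance. A true trough of 10 that reads 7.6 to 8.7 also stays within the 5–15 range of DSMB question 1, although it falls below the 10–15 range of Table 2. Misreading matters mainly near the limits, and the documents do not show how many levels would fall there.

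**What to change.** In section 9.1 and in Table 3, footnote 2, replace the 24-hour wording with: *immediately before the morning dose, about 12 hours after the last dose*.

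Apply this explicitly to the day 7 and day 14 troughs. Sections 9.1 and 11.2 list day 7 sampling only at +1 and +3 hours after a dose, while calling the result a trough. Those samples serve the PK model but are not troughs, so the day 7 adjustment needs a pre-dose sample.

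If any level has already been drawn at about 24 hours, show the actual time since the last dose beside it in the DSMB report. The CRF already collects what is needed.

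The cost is a short amendment in two places, plus asking families to hold the morning dose until the draw. No extra visit is needed and no dose is omitted. If no pre-dose sample is now taken on day 7, one more small sample is needed at a visit that already has two.

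It would be a mistake to add a rule that counts a level as steady state only after at least 7 days on an unchanged dose. Section 9.1 does not require an unchanged dose, and it allows only 6 (±1) days on the adjusted dose before the day 14 level. Such a rule would discard most of the day 14 troughs on that schedule.

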## 9.2 CONCURRENT MANAGEMENT OF EPILEPSY

The purpose of the study is to determine if sirolimus is safe and effective for prevention of epilepsy in at-risk infants diagnosed with TSC. The primary endpoint for efficacy epilepsy prevention is time to first seizure (seizure onset). However, subjects treated with sirolimus may still develop seizures if (1) our primary hypothesis is incorrect and sirolimus is not preventative or (2) our hypothesis is correct and seizure onset is delayed but sirolimus does not fully eliminate seizures from ever occurring. It is this very reason that our study will evaluate additional secondary efficacy disease-modifying outcome measures relating to epilepsy (seizure type and seizure frequency) and neurodevelopment at 12 months of age.

Accordingly, new onset of seizures (clinical or electrographic) does not require discontinuation of study medication. New onset of seizures should be evaluated and treated with conventional anticonvulsant medications (note that mTOR inhibitors are excluded) according to recommended clinical practice guidelines and the managing clinician's best judgement. In most instances, this will be initiation of vigabatrin, recommended first line therapy for infantile spasms in TSC and an effective treatment for focal epilepsy which is also common at this age. Rescue medications are also allowed. In all instances, prescribed treatment for seizures (medication, diet, and/or procedures) will be recorded in the appropriate CRF, including medication/treatment/procedure name, start/end dates used, total daily dose prescribed (including dosage adjustments, when applicable). Medications temporarily utilized or prescribed for use on as needed basis (PRN) will be recorded and include the date/time/dose for each use.

Another clinical scenario with relevance to the current study is the potential for off-label, prophylactic treatment with vigabatrin in TSC infants who have not yet experienced clinical or electrographic seizures. Off-label prophylactic treatment with vigabatrin has the potential to directly interfere with primary and indirectly affect secondary outcome measures of this study evaluating the preventative benefit of sirolimus. Jóźwiak et al (2011) published a case series of 14 TSC infants prophylactically treated with vigabatrin following abnormal EEG, compared to

historical controls treated conventionally with vigabatrin after the onset of clinical seizures. In that study, the pre-emptive vigabatrin treatment did not always prevent seizures from occurring but still resulted in favorable seizure control and developmental outcomes at 24 months of age. Some patients since 2011 as a result have been treated with prophylactic vigabatrin in the absence of clinical or electrographic seizures. However, the Jóźwiak study results have yet to be replicated and validation efforts using prospective, randomized, double-blind clinical trials currently are underway in Europe (EPISTOP) and the United States (PREVeNT). Until then, off-label prophylactic treatment with vigabatrin is not recommended in current international guidelines nor considered current standard of care. Accordingly, such prophylactic treatment with vigabatrin (or any other anticonvulsant medication or anti-seizure therapy prescribed for the same purpose of epilepsy prevention) before the onset of first seizure is specifically prohibited. To be clear, this restriction does not apply to vigabatrin or any other anticonvulsant or anti-seizure treatment(s) after the onset of first clinical seizure (see above), as withholding such treatment would be unethical and contrary to current treatment guidelines.

# **10 STUDY DRUG SUPPLY**

## 10.1 Description of Study Drug

The investigational drug product to be used in this study is TAVT-18, a proprietary formulation of sirolimus in clinical development, by Tavanta Therapeutics, Inc. It is provided in powder formulation consisting of 16.7% sirolimus as active ingredient along with 50.0% Povidon K90 and 33.3% sodium lauryl sulfate as excipients. The excipients ensure that sirolimus disperses instantaneously in water, which is then administered as an oral solution. Both excipients used are pharmaceutical grade and are listed on the FDA Inactive Ingredients Used in Approved Drug Products list. TAVT-18 will be supplied from the manufacturer in powder form in premeasured vials. The central investigational pharmacy at Cincinnati Children's will then oversee the labeling of the TAVT-18 in pre-measured vials containing 500 ug of TAVT-18 (sirolimus) for single use. TAVT-18 is stable in powder form for at least 12 months when stored at 2-8 °C.

Printed instructions and supplies will be provided to the parent for TAVT-18 preparation and administration. When not in use, TAVT-18 (sirolimus) will be kept in the refrigerator. At time of administration, the parent/caregiver will add 20 ml water and invert the vial 2-3 times to reconstitute the oral solution with a concentration of 0.025 mg/ml. The reconstituted solution is ready for administration right after the reconstitution and is stable at room temperature for at least 2 hours. Sirolimus stability is known to be reduced at lower pH (e.g. pH <3) that is ameliorated by raising pH by as little as 1-2 points. Stomach pH in infants typically ranges between 2-5 and although there was little difference between fasted and fed states with regard to mean  $t_{max}$  (< 1 hr) in adults treated with TAVT-18 (sirolimus), we want to reduce this potential added source of absorption variability to the present study. Accordingly, TAVT-18 (sirolimus) will be administered to infants in the fed state (within 30 minutes of feeding), where breastmilk or formula (pH 7.0-7.4) is sufficient to sufficiently raise stomach pH above the minimum desired threshold (pH > 4).

## 10.2 Study Drug Labelling and Packaging

TAVT-18 will be packaged and labeled per institutional guidelines. Study medication labels will be labeled as "Sirolimus (TAVT-18) for Oral Solution" and include all additional required labeling as an investigational product, including source (Cincinnati Children's Hospital),

quantity, administration instructions, storage conditions, Lot#, Expiration date, Name of Clinical Trial, PI Name, and FDA IND#.

## 10.3 Study Drug Administration, Compliance and Accountability

Medication will be dispensed to subjects at each visit, with enough supply to cover the visit window time period. Subjects will be instructed on how to prepare and administer study drug in accordance with the protocol. Dispensing of study drug will only be done by designated and qualified individuals at that site location. The study drug is to be taken as a suspension only. For PK/PD analyses, time and dose amount will be captured via CRF when corresponding blood trough levels are obtained (see section 9 above regarding dosing and blood trough level monitoring). An IRB-approved Dosing and Administration instructions for use will be provided to subject families that outlines specific instructions for preparation and use.

If the subject misses a dose (scheduled dose not administered within 12 hours of expected timing), the dose will be skipped. The missed dose will be recorded as not taken in the subjects' medication diary. If the dose is missed/held due an AE, that will be recorded in the subject's medication diary also. Study drug compliance will be assessed by the investigator and/or study team designee at each visit. Parents/LARs will be expected to return both unused and used study drug to the site at each scheduled visit. All doses taken and any adjustments in doses are to be captured on the drug diary CRF.

Subjects who take 75-125% of their drug, excluding days in which they are instructed to temporarily hold study medication by study investigators due to an AE (see section 12), will be considered compliant. Subjects who take <75% or > 125% of their drug, excluding days in which they are instructed to temporarily hold study medication by study investigators due to an AE (see section 12), or subjects for which drug compliance cannot be verified, may be withdrawn from the study (see section 8.3 above).

Upon withdrawal from or completion of the study, any unused study medication is to be returned by the subject.

